**Short running title: *Nurse Led Transitional Care Model in Cardiac Surgery***

**25.05.2017**

## **BACKGROUND**

Rate and number of successful cases in open heart surgery has been increasing due to the advances in medical technology and surgery. To improve patient convalescence results and reduce rate of post-discharge readmission to hospital and unplanned post-discharge rehospitalization, home-care and follow-up process of patients should be managed successfully. We have not come across examples of a care model in literature that has actively been used on elderly patients undergoing open heart surgery in Turkey. However, in practice, patients undergoing open heart surgery are discharged from the hospital in an average of 4-5 days which is a period retaining patients and their families to experience a successful post-op transition process. Finally, all of these can provide a basis for the problems that patients undergoing open heart surgery and their relatives may experience throughout post discharge healthcare. In addition, problems due to increased health care expenses may arise in line with the repeated post discharge referrals to hospital and rehospitalization rates.

In this study we have used a Transitional Care Model (TCM) developed by Mary Naylor basically for elderly patients undergoing open heart surgery, aiming to support defenseless/vulnerable elderly individuals with chronic diseases and their families and to prevent problems that cause an increase in repeated post discharge referrals to hospital and rehospitalization rates and aimed to evaluate the effect of the model on the quality of life, functional autonomy and repeated post discharge referrals to hospital and rehospitalization rates of elderly patients undergoing surgery.

### **Aim of the study and hypotheses**

The purpose of this study is to evaluate the effectiveness of the Nurse Led Transitional Care Model. The hypotheses are as follows;

H0: Nursing care carried out in collaboration with a multidisciplinary team in line with TCM for elderly patients who have undergone open heart surgery has no effect on decreasing the patients' functional autonomy, their quality of life levels and the rate of repeated post discharge referrals to hospital and rehospitalization.

H1: Nursing care carried out in collaboration with a multidisciplinary team in line with TCM for elderly patients who have undergone open heart surgery may improve the patients' functional autonomy, their quality of life levels and decrease the rate of repeated post discharge referrals to hospital and rehospitalization.

## **STUDY PROTOCOL**

### **1 | Study design**

The research was carried out between November 2017 and December 2018 in a pretest-posttest design structured in accordance with the CONSORT guidelines (Figure 1), as a randomized controlled intervention study with parallel groups (Schulz, Altman, & Moher, 2010).

### **2 | Study participants and allocation**

The study was carried out in an 11-bed cardiovascular surgery clinic of a university hospital located in the Black Sea Region of Turkey with a total capacity of 320 beds. The group of patients aged 60 and over, who were hospitalized for open heart surgery, constituted the universe of the study.

#### **2.1 | Inclusion and exclusion criteria**

Inclusion criteria for participation in the study are as follows: The Patient should a) be hospitalized for the first time and for elective open heart surgery; b) have no other surgical intervention other than an open heart surgery, c) have no psychological and mental disorders, d) have no major chronic problems such as kidney problems, neurological problems or cancer, e) be able to speak Turkish, f) be available to be communicated by phone, g) provide consent to participate in the study, h) live at a maximum distance of 50 km from the hospital (for easy access during post-discharge follow-up visits). Exclusion criteria are as follows: The Patient should a) ask to leave the study, b) be exposed to a disease or trauma that may affect his/her functional autonomy during the study, c) die throughout the study.

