## **3.Data Collection**

### **3.1 | Enrollment**

A Ph.D. student and research assistant with clinical experience as a nurse for five years in the cardiovascular surgery clinic evaluated the participants who are decided to undergo an open heart surgery at their admission to the service and assigned those who met the application criteria to intervention and control groups respectively.

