### **3.2 | Allocation**

Patients were randomly assigned to the intervention and control groups respectively in line with the inclusion criteria of sampling through a computerized randomization system. Patients reached in the pre-application period (n = 6) were also included in the sample of the study, considering possible patient loss throughout the study. Ultimately, 66 patients were included in this study; the subjects were individually numbered and randomized by an individual outside of the investigation team using the website software program Research Randomizer

(<http://www.random.org>) to divide the subjects into the intervention group (33 patients) and control group (33 patients). The patients were not blinded. If someone declined, the next patient from the list was invited instead.

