### **3.5 | Intervention**

Patients in intervention group were given care based on the 'Nurse Led Transitional Care Model Protocol' (Figure 2) until the post discharge 9th week starting from date of hospitalization. Patients in control group were given standard care services.

The patients in both groups were interviewed face-to-face by the Researcher (Coordinator Nurse) in the first twenty-four hours following their admission to the hospital and administered "Introductory Information Form", "The Functional Autonomy Measurement System" and "SF-36 Quality of Life Scale". In addition, the Researcher (Coordinator Nurse) reached the patients in both groups after nine weeks following their discharge and reapplied the "The Functional Autonomy Measurement System" and "SF-36 Quality of Life Scale". Six months following their discharge these patients were called by phone and checked up on their repeated referrals to hospital and/or rehospitalization.

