### **3.6 | Statistical methods**

The data obtained throughout the study were evaluated by statistical analyzes (using IBM SPSS Statistics 23 software). Parametric tests were leveraged while evaluating research data based on the argument of Law of Large Numbers stating that (İnal & Günay, 2002) “The average of the results obtained from a large number of trials  $n \rightarrow \infty$  will tend to become closer to the expected value”. The evaluation of the research data provides frequency distribution (number, percentage) for categorical variables and descriptive statistics (mean, standard deviation) for numerical variables. Difference between categorical variables with two groups was tested using Independent t-Test whereas the difference between the categorical variables with more than two groups was tested with "One Way Variance Analysis" (ANOVA). Following the analysis; initially, the homogeneity of the variance was controlled by Levene Test and then the group or groups causing the difference were controlled by "Multiple Comparison Test". The difference between the groups regarding the variables that provide variance homogeneity was evaluated via Bonferonni while Tamhane's T2 test was used to examine the difference between groups in variables that do not comply with variance homogeneity. In addition, the difference between the two numerical variables over time was evaluated with Dependent Sample t Test while the relationship between the two categorical variables was examined with the Chi-Square test. Statistical significance was considered as  $p < 0.05$ .

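### Section 2.1 removes randomised patients for illness, trauma or death during follow-up, and Section 3.6 defines no analysis population or rule for deaths to offset this

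*Combined protocol and SAP*

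**What the plan says.** Section 3.1 has the research nurse screen patients "at their admission to the service and assigned those who met the application criteria to intervention and control groups", so assignment precedes surgery, discharge and follow-up. Section 3.2 gives 33 patients per arm.

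Section 2.1 lists three exclusion criteria. One is a request to leave the study. The other two apply to a patient who should "be exposed to a disease or trauma that may affect his/her functional autonomy during the study, c) die throughout the study".

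The outcomes in the hypotheses are functional autonomy, quality of life, and a wish to "decrease the rate of repeated post discharge referrals to hospital and rehospitalization". Under Section 3.5, the functional autonomy scale and SF-36 are repeated nine weeks after discharge in both arms. At six months both arms are telephoned and "checked up on their repeated referrals to hospital and/or rehospitalization".

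Section 3.6 lists t-tests, ANOVA with post hoc tests, chi-square and a significance level of 0.05. For change over time, "the difference between the two numerical variables over time was evaluated with Dependent Sample t Test". It does not say which patients are analysed, how missing scores are treated, or how deaths enter the analysis. The only provision for losses is in Section 3.2, where the six pre-application patients are kept in the sample, "considering possible patient loss throughout the study".

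**The concern.** Exclusion criteria normally decide who enters a trial. These describe things that happen to patients already in it. The illness-or-trauma criterion selects on a cause of poor functional autonomy, which is an outcome. Such an illness may also put the patient back in hospital, so the same rule can remove rehospitalisation events.

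There are two reasons why exclusions might differ by arm, and they point in opposite directions:

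- The model is meant "to prevent problems that cause an increase in repeated post discharge referrals to hospital and rehospitalization rates". If it works, fewer intervention patients would meet the criterion.
- Figure 2 gives intervention patients home visits within 24 hours of discharge and at weeks 2, 6 and 9, plus telephone advice in week 1. For controls, Section 3.5 says "Patients in control group were given standard care services" and adds only the week-9 assessment and the six-month call. Closer observation could reveal more qualifying illness in the intervention arm.

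The criterion needs judgement, because the illness need only be one that might affect autonomy. The documents do not say who decides, whether data already collected are removed, or whether the study period ends at week 9 or month 6. Section 3.2 says that patients were not blinded.

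Death is not a listed outcome. It prevents a week-9 score if early and prevents later rehospitalisation at any time. Excluding deaths leaves this truncation or competing-event problem with no analytic handling.

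**Working it through.** **Which text governs.** Assignment is at admission (3.1). Illness or trauma during the study and death are follow-up events (2.1). A request to leave could occasionally come before assignment, but mostly comes after it. No section says that excluded patients stay in the analysis. The paired t-test in 3.6 can use only patients with both scores. The six additional patients (66 against 60, or 33 against 30 per arm) protect the sample size, but they do not restore comparability.

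The plan gives no exclusion or event rates, so there is no stated figure to reproduce. What follows shows possible size under assumptions.

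**Illustration 1: rehospitalisation.** Let *p* be the true proportion rehospitalised and *s* the share of rehospitalised patients who are excluded, with nobody else excluded. The observed proportion is *p*(1 − *s*) / (1 − *ps*). For example, *p* = 0.30 and *s* = 0.25 gives 0.225 / 0.925 = 24.3%. With *s* = 0.50 it is 0.150 / 0.850 = 17.6%. For *p* = 0.15 the two results are 0.1125 / 0.9625 = 11.7% and 0.075 / 0.925 = 8.1%.

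| True control v intervention | Share excluded, control v intervention | Observed | Difference (points) |
|---|---|---|---|
| 30% v 15% | none | 30.0% v 15.0% | 15.0 |
| 30% v 15% | 25% v 25% | 24.3% v 11.7% | 12.6 |
| 30% v 15% | 50% v 50% | 17.6% v 8.1% | 9.5 |
| 30% v 15% | 25% v 50% | 24.3% v 8.1% | 16.2 |
| 30% v 15% | 50% v 25% | 17.6% v 11.7% | 6.0 |
| 30% v 30% | 25% v 50% | 24.3% v 17.6% | 6.7 |
| 30% v 30% | 50% v 25% | 17.6% v 24.3% | −6.7 |

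Differences are taken before rounding. Equal exclusion dilutes a real effect. Unequal exclusion can enlarge it, shrink it or create one. If exclusion affects only the week-9 scales and not the six-month data, this illustration does not apply.

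**Illustration 2: a continuous scale with no true effect.** Inputs are 33 per arm (3.2), standard normal outcomes, a two-sided pooled t-test at 0.05 (3.6 gives 0.05 but not sidedness) and 60,000 simulated trials per setting. In each arm the *k* patients lowest on an exclusion score are removed. The score correlates with the outcome either 0.5 or 1; a correlation of 1 is the worst case, in which exactly the lowest scorers go.

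| Removed per arm | False difference, corr. 0.5 | Type I error, corr. 0.5 | False difference, worst case | Type I error, worst case |
|---|---|---|---|---|
| 0 v 0 | 0 | 5.0% | 0 | 5.0% |
| 3 v 1 | 0.054 SD | 5.9% | 0.106 SD | 9.5% |
| 4 v 1 | 0.077 SD | 6.5% | 0.155 SD | 12.6% |
| 3 v 3 | 0.00 SD | 5.7% | 0.00 SD | 8.0% |

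The 3 v 3 row shows that part of the inflation comes from trimming alone. Three losses in an arm equals the plan's own margin of 33 − 30 = 3.

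**The case against.** The strongest reply is that loss of data is inferred. Section 2.1 could be read as a list of events that end participation, and no section says that data already collected are discarded. Section 1 cites CONSORT, and Figure 1, a flow diagram not visible in the text available to us, might show 33 v 33 analysed, in which case nobody was lost. This stands as a limit on what can be claimed: actual harm is unknown. It does not answer the point, because a patient listed as excluded is naturally read as out of the analysis and nothing says otherwise. A flow diagram can report losses, but it cannot restore them.

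The illustrations rest on assumed rates, and the moderate case is small. At correlation 0.5 the type I error is 5.9% to 6.5%, and a false difference of 0.05 to 0.16 SD compares with a standard error of √(2/33) ≈ 0.25 SD. A fairer comparator for 3 v 1 is 2 v 2, with the same total removed. That gives about 5.3% (correlation 0.5) and 7.2% (worst case), so imbalance itself adds about 5.9 − 5.3 = 0.6 and 9.5 − 7.2 = 2.3 points. This is fair, and the upper figures should be read as a bound.

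The detection argument is conjecture, since both arms are contacted at week 9 and month 6. That is right; it shows only that unequal exclusion is plausible. It is also true that deaths are not wholly unaddressed, because Section 2.1 excludes them. What is missing is any way of dealing with them in the analysis.

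Finally, the document is written in the past tense for a study run from November 2017 to December 2018, so rewording the criteria cannot change what was done. This affects the form of the remedy, not the need for one.

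**Conclusion.** The concern holds. The plan contains a rule that, if followed, removes randomised patients for events tied to a named outcome, and no stated analysis population corrects for it. This is more than a missing detail, and recruiting more patients would not cure it. It must be fixed.

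The size and direction of bias cannot be determined from the documents, and if nobody was excluded the effect is nil. Under the assumptions shown, a true 15-point rehospitalisation difference could appear as anything from 6.0 to 16.2 points, and a null effect as 6.7 points in either direction. Type I error on a scale score could rise from 5% to between about 6% and 12.6%, with the upper end reached only in the worst case. Confidence is high that the rule and the gap exist; the illustrations are not estimates of what happened.

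**What to change.** - **Section 2.1.** Remove illness or trauma during the study, and death, from the exclusion criteria. Treat a request to leave as withdrawal. This concerns who is analysed; it does not touch how an ill patient is cared for.
- **Section 3.6, population.** State that all randomised patients are analysed in their assigned arm. Week-9 scores and six-month referral and rehospitalisation data should be used whatever illness or trauma occurred, and data up to withdrawal or death should be kept.
- **Section 3.6, deaths.** Report deaths by arm beside rehospitalisation, and name one sensitivity analysis. Rehospitalisation or death as a composite, or a worst score for patients who died, are two options.
- **Reporting.** Give exclusions and missing data by arm and reason, including the number excluded under each criterion. If that number is zero, say so.

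If data collection is complete, as the tense of the document suggests, the practical step is to restore the data already collected on excluded patients, re-analyse, disclose the rule that was applied, and list as a limitation any week-9 scores never taken. Those cannot be recovered.

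The cost before analysis is a wording change to two sections. No patients or visits are added, because both arms already have the week-9 assessment and the six-month call. Afterwards the cost is a re-analysis and disclosure. The drawback is slightly more variable scores and a little more analysis.

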## **3.Data Collection**

### **3.1 | Enrollment**

A Ph.D. student and research assistant with clinical experience as a nurse for five years in the cardiovascular surgery clinic evaluated the participants who are decided to undergo an open heart surgery at their admission to the service and assigned those who met the application criteria to intervention and control groups respectively.

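### Section 2.1 excludes patients for events that can follow assignment and section 3.6 sets no analysis by assigned arm; secondarily, 3.1 and 3.2 differ on who assigned patients

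*Combined protocol and SAP*

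**What the plan says.** **Exclusions.** Section 2.1 reads: "Exclusion criteria are as follows: The Patient should a) ask to leave the study". The other two grounds are "be exposed to a disease or trauma that may affect his/her functional autonomy during the study, c) die throughout the study".

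**Timing.** Section 3.1 has patients screened and assigned at admission, and section 3.5 starts the intervention from the date of hospitalisation. Section 3.5 repeats the functional autonomy and SF-36 scales nine weeks after discharge and asks about referrals and rehospitalisation at six months.

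**Outcomes and analysis.** H1 names functional autonomy, quality of life, and repeated referrals and rehospitalisation. Section 3.6 lists tests and a 0.05 significance level. It defines no analysis population and no handling of withdrawals, deaths or missing scales.

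**Allocation.** In section 3.1 the research assistant who checked eligibility also "assigned those who met the application criteria to intervention and control groups respectively". In section 3.2 patients were "randomized by an individual outside of the investigation team using the website software program Research Randomizer". Section 3.2 adds: "If someone declined, the next patient from the list was invited instead". It also includes the six pre-application patients, "considering possible patient loss throughout the study", and counts 66 patients, 33 per arm.

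**The concern.** Randomisation protects the comparison only if the patients compared are the patients randomised. Section 2.1 states a removal rule, not merely a gap. Its second ground depends on something that may affect an H1 outcome, and such an illness or injury may also cause a readmission. Patients were not blinded, so requests to leave may differ by arm. Intervention patients also receive the home visits in Figure 2 while controls receive standard care, so a new illness might be noticed more readily in one arm. With 33 per arm, a few unequal removals can move an estimate.

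The secondary issue is allocation. If the person judging eligibility could see the next arm, borderline decisions could be affected. The criterion "have no major chronic problems such as kidney problems, neurological problems or cancer" leaves room for judgement. The visible text does not say whether this was possible.

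**Working it through.** **1. Can the exclusion events follow assignment?** Assignment is at admission (3.1), before surgery. Outcomes fall nine weeks and six months after discharge (3.5). Leaving, new disease or trauma, and death can each fall in between.

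**2. Does 3.6 undo the exclusions?** No. It gives no rule to keep patients in the assigned arm, so 2.1 is the only instruction on what happens to them.

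**3. Which outcomes could be lost?** Under the disease or trauma ground: the 9-week scales and any readmission. Under death: only referrals and readmissions before it. Death is not an H1 outcome, and a patient who dies before week 9 has no 9-week scale to remove.

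**4. Readmission, illustrative.** The plan gives no base rate. Assume the same count b of 33 in each arm, no true effect, and three patients excluded from one arm only.

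| b | Full arm | All 3 had been readmitted | None had been |
|---|---|---|---|
| 7 | 7/33 = 21.2% | 4/30 = 13.3%, false benefit 7.9 points | 7/30 = 23.3%, false disadvantage 2.1 |
| 10 | 10/33 = 30.3% | 7/30 = 23.3%, false benefit 7.0 | 10/30 = 33.3%, false disadvantage 3.0 |
| 13 | 13/33 = 39.4% | 10/30 = 33.3%, false benefit 6.1 | 13/30 = 43.3%, false disadvantage 3.9 |

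**5. Scale scores, illustrative.** Assume a standard normal outcome, no true effect, 33 per arm, and k patients drawn at random from the lowest 16 of one arm on a trait with correlation r to the outcome. The shift is about r × k × m/(33 − k), where m is the mean distance of the lowest 16 of 33 below the centre, about 0.80 SD. For r = 1: k = 3 gives 3 × 0.80/30 = 0.08 SD, and k = 5 gives 5 × 0.80/28 = 0.14 SD. Simulation (100,000 trials per setting, two-sided t-test at 5%) agrees:

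| k | r = 1 | r = 0.5 | r = 0.3 |
|---|---|---|---|
| 3 | 0.08 SD, error 5.8% | 0.04 SD, 5.3% | 0.02 SD, 5.1% |
| 5 | 0.14 SD, 8.0% | 0.07 SD, 5.6% | 0.04 SD, 5.2% |

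At r = 0 there is no bias and the error is 5.0%. A harsher mechanism, removing the worst outcomes themselves from one arm, gives 0.07, 0.12 and 0.17 SD for one, two and three patients, with error 6.3%, 8.8% and 12.2%. None of these scenarios is a bound.

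**6. Allocation accounts side by side.** Section 3.1 makes the screener the assigner; 3.2 makes it a person outside the team. They fit together if the outsider generated the list and the research assistant carried it out. Even then, no visible text says who held the list, who released each assignment, or whether baseline came first: 3.5 places baseline within 24 hours of admission and 3.1 places assignment at admission. Consent ("provide consent to participate in the study") is an inclusion criterion, so refusals most naturally came before assignment, but the replacement sentence does not say so. For scale only: passing over half of the lowest-quarter candidates for one arm (about 5 patients) would shift the difference by 0.18, 0.09 or 0.05 SD at r = 1, 0.5 or 0.3, with error 12.0%, 6.6% or 5.6%.

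**The case against.** The strongest reply is that nothing visible shows harm. Section 2.1 does not say outright that excluded patients' data were discarded. No counts are given. The study is described as following CONSORT, and Figure 1, its flow diagram, may show the order of enrolment and allocation, losses by arm and numbers analysed. At correlations of 0.3 to 0.5 with three exclusions, type I error is 5.1% to 5.3%, practically nominal, and every scenario is one-sided by assumption. All of that stands, and it limits the point to a risk created by the rule as written.

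Three stronger readings are tempting, and the documents do not support them.

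- *The screener assigned arms without concealment.* Section 3.2 says an outside individual randomised by computer, so the two sections conflict or need joining. Silence on concealment does not show that it was absent.
- *The six pre-application patients were not randomised.* Section 3.2 implies they are among the 66; only when they were randomised relative to the rest is unstated.
- *Excluding deaths removes an outcome under test.* H1 does not count death.

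What the reply does not answer is that 2.1 excludes patients for later events, one of them tied to an H1 outcome, and 3.6 does not restore them.

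**Conclusion.** The main point holds: followed as written, 2.1 and 3.6 allow the arms compared to differ from the arms randomised. Bias is possible, not shown. Its size cannot be derived from the documents. Under the assumed one-arm scenarios, three exclusions move a readmission comparison by 6.1 to 7.9 points one way or 2.1 to 3.9 the other. They move a scale score by 0.02 to 0.08 SD, or 0.17 SD if the three worst outcomes are the ones removed. These figures rest on assumed correlations, counts and base rates. They show what a few patients can do at this sample size, not what happened.

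The allocation point is secondary. It is a conflict between 3.1 and 3.2 plus missing detail on concealment, which calls for reconciliation and reporting. It does not establish that allocation was compromised.

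**What to change.** **Section 2.1.** Reclassify leaving, new disease or trauma, and death as withdrawal or follow-up events, not exclusions.

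**Section 3.6.** State that every randomised patient is analysed in the assigned arm. Use all available 9-week scales and all referrals and rehospitalisations up to six months, including those before death or withdrawal where consent allows. Report deaths, withdrawals and missing scales by arm. Call this an available-data analysis by assigned arm, since patients with missing scales still drop out of the scale comparisons.

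**Sections 3.1 and 3.2.** Reconcile them into one account. Report who held and released the list, whether the next arm was hidden from the screener, the order of consent, baseline and assignment, whether replacement came only before assignment, and when the six pre-application patients were randomised. Section 1 is in the past tense, so if allocation is complete, concealment cannot be added, but the analysis rule and the reporting still can.

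**Cost.** Wording changes and a little more analysis and reporting, with no loss of sample size relative to the current exclusions. Scales that go missing are missing under either rule. Three per arm would leave 30, the target in 3.3. At 80% power (an assumption; 3.3 states no power) and two-sided 5%, the detectable difference is 0.70 SD with 33 per arm, 0.74 SD with 30 and 0.76 SD with 28, and the fix does not cause that loss.
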